8.3.5.1. Pregnancy Testing

A serum pregnancy test will be required for all women of childbearing potential during screening and at the follow-up visit. Urine pregnancy tests will be performed locally, as outlined in **Table 4**, as medically indicated (eg, in case of loss of menstrual cycle, when pregnancy is suspected). If a urine pregnancy test is positive, the results should be confirmed with a serum pregnancy test.

If the serum pregnancy test is negative after a urine test was positive, the investigator will assess the potential benefit/risk to the participant and determine whether it is in the participant's best interest to resume study drug and continue participation in the study.

[figure not shown]
If a pregnancy is confirmed by a serum pregnancy test, see Section [9.6](#) for reporting requirements.

8.3.5.2. Serology and Virology

Hepatitis and HIV assessments will be performed at the screening visit to rule out hepatitis or HIV infection; required analytes are shown in [Table 10](#). Serology and virology tests should be performed early in the screening process due to the length of time needed to obtain the results. Additional tests may be performed if clinically indicated.

8.3.5.3. Tuberculosis Testing

Tuberculosis B assessments will be performed at the screening visit. Test must be performed using the QuantiFERON-TB Gold test or T-SPOT.TB test. If there are 2 indeterminate tests, evaluation by a purified protein derivative test with a result of < 5 mm of induration must be conducted within 3 months of screening.

8.5. Pharmacodynamic and Translational Assessments

Peripheral blood samples (eg, serum, PBMC, RNA), tear samples, and saliva samples will be collected from participants at timepoints outlined in [Table 4](#). All samples for PD and translational assessments will be collected before INCB050465 administration.

[REDACTED] All analyses will be conducted by Incyte Corporation (Wilmington, DE) or Incyte's designee. Information regarding handling/shipping of specimens will be provided in the Laboratory Manual.

8.6. End of Treatment

If a decision is made that the participant permanently discontinues study drug (early termination) or has completed the Protocol-specified duration of treatment, then an EOT visit should be conducted. If the EOT visit coincides with a regular study visit, the EOT evaluations will supersede those of that scheduled visit, and the data should be entered in the EOT visit in the eCRF. The participant should be encouraged to return for the safety follow-up visits.

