This is an open-label, Phase 2 study to assess the impact of PI3K δ inhibitor INCB050465 on signs and symptoms of SS. A single group of 12 participating adults, \geq 18 years old, who meet the inclusion criteria, will be enrolled for a duration of 12 weeks (with a 30-day safety follow-up period) and receive treatment with INCB050465 1.0 mg QD. Participants will undergo ultrasound measurement of salivary glands, measurements of salivary flow, collection of symptom questionnaires, and PD [REDACTED] blood sampling to allow studies of cytokine levels, gene expression levels, and other PD markers.

The study design is shown in [Figure 1](#).

Adherence to the study design requirements, including those specified in the SoA, is essential and required for study conduct.

[Table 3](#) provides the SoA for the study, and [Table 4](#) provides a Schedule of Laboratory Assessments.

Table 3: Schedule of Activities

	Screening (Day -28 to Day -1)	Day 1	Week 2 (± 3 Days)	Week 4 (± 7 Days)	Week 8 (± 7 Days)	Week 12/ EOT (± 7 Days)	Safety Follow-Up (30 Days [+7 Days] After Last Dose of Study Drug)	Comments
Administrative Procedures								
Informed consent	X							
Contact IRT	X	X	X	X	X	X		
Inclusion/exclusion criteria	X	X						
Medical and medication history	X							
Concomitant medications	X	X	X	X	X	X	X	
Dispense reminder card		X	X	X	X			
Administer study drug during visit		X	X	X	X			
Dispense study drug		X	X	X	X			
Drug accountability and compliance assessment			X	X	X	X		
Administer PJP prophylaxis if needed*		X	X	X	X	X	X	From Day 1 to at least 30 days after last dose of study drug. *See Section 6.6.1.1.
Safety Assessments								
AE assessment	X	X	X	X	X	X	X	
Comprehensive physical examination	X						X	
Targeted physical examination		X	X	X	X	X		Body systems with symptoms should be physically examined.
Vital signs	X	X	X	X	X	X	X	Measure height at screening only.
12-lead ECG	X	X	X			X	X*	*Standard ECG.
Efficacy Assessments								
Ultrasound of parotid and submandibular salivary glands		X*		X		X		*Schedule ultrasound 2 weeks before Day 1 to ensure results availability.
Measurement of total unstimulated salivary flow	X	X		X	X	X		
Measurement of total stimulated salivary flow	X*	X		X	X	X		*Documented measurement within 12 weeks before screening visit.
Questionnaire for dryness of eyes, mouth, and (females only) vagina	X	X		X	X	X		
ESSDAI assessment	X	X		X	X	X		
ESSPRI questionnaire	X	X		X	X	X		
PGIC questionnaire	X	X		X	X	X		

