PJP prophylaxis: Prior treatment with prednisone or equivalent may represent a risk factor for PJP in combination with other immunosuppressants. Participants who have received prednisone \geq 20 mg per day (or equivalent) within 60 days before baseline are excluded. Participants receiving \geq 10 mg to $<$ 20 mg of prednisone (or equivalent) may be at increased risk for PJP, and prophylaxis should be considered for these participants, particularly if they have a history of PJP or have recently received any immunosuppressive therapy that may represent an increased risk. Participants receiving $<$ 10 mg of prednisone or equivalent have some potential risk. PJP prophylaxis is not required for these participants but should be considered by the investigator only in exceptional circumstances in consultation with the medical monitor as needed.

Examples of standard PJP prophylaxis therapies include trimethoprim-sulfamethoxazole, atovaquone, dapsone with or without pyrimethamine, and pentamidine ([Baden et al 2012](#)). Due to reports of cross-sensitivity between sulfonamides and dapsone, all participants who have a known or suspected allergy to sulfonamides must receive either inhaled pentamidine or atovaquone for PJP prophylaxis. Prophylaxis should be given while participants are receiving study drug and should continue for at least 30 days after the last dose of study drug.

In addition to these study visits, there will be laboratory-only visits at the end of Week 2 to collect safety laboratory assessments [REDACTED].

Week 12 will correspond to the EOT. A safety follow up visit will occur 30 (+7) days after the last dose of study drug.

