7.1.2. Discontinuation Procedures

In the event that the decision is made to permanently discontinue the study treatment, the EOT visit should be conducted. Reasonable efforts should be made to have the participant return for a follow-up visit. These visits are described in [Table 3](#) and [Table 4](#). The last date of the last dose of study drug(s)/treatment and the reason for discontinuation of study treatment will be recorded in the eCRF.

If a participant is discontinued from study treatment:

- The study monitor or sponsor must be notified.
- The reason(s) for withdrawal must be documented in the participant's medical record and the primary reason for withdrawal must be included in the eCRF.
- The EOT visit should be performed.
- The date of the EOT visit should be recorded in the eCRF.

- Participants must be followed for safety until the time of the follow-up visit or until study drug-related toxicities resolve, return to baseline, or are deemed irreversible, whichever is longest.

If the participant discontinues study treatment and actively withdraws consent for collection of follow-up data (safety follow-up) then no additional data collection should occur; however, participants will have the option of withdrawing consent for study treatment but continuing in the follow-up period of the study for safety assessments.

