8.2. Efficacy Assessments

8.2.1. Ultrasound of Salivary Glands

Ultrasound measurement of the parotid and submandibular glands will be performed at visits indicated in [Table 3](#). Ultrasound of glands will be performed in the longitudinal and transverse planes with participants in a supine position. The ultrasound images will be images will be evaluated for quality then transmitted to a central vendor for reading and data summarization. The echostructure of each gland on B-mode images will be graded on a 5-point scales (0 to 4) as described by [Gazeau et al 2018](#). Grade 0 indicates a normal homogeneous gland, Grade 1 small hypoechoic areas with hyperechoic bands, Grade 2 multiple hypoechoic areas less than 2 mm, Grade 3 multiple hypoechoic areas 2 to 6 mm, and Grade 4 multiple hypoechoic areas larger than 6 mm. For each participant at each timepoint, 4 grades will be obtained, one for each parotid and submandibular gland. The SGUS score is the numeric sum of the 4 individual grades. [REDACTED]

[REDACTED] Instructions for conducting and transmitting ultrasound measurements will be provided in the Study Manual.

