8.2.4. Patient-Reported Outcomes

Patient-reported outcome instruments will be given to participants for completion at study visits indicated in [Table 3](#). Site staff will enter completed questionnaires into the eCRF database.

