10.4.1. Efficacy Analysis

Efficacy assessments will be summarized using descriptive statistics at each visit.

For the primary endpoint, proportion of participants with 1 point or greater improvement on the SGUS for parotid and submandibular glands, as well as the secondary endpoint of PGIC, summary statistics will include sample size, frequency, and percentages.

For all other measurements in the secondary endpoints, which are continuous, summary statistics will include sample size, mean, median, standard deviation, standard error of the mean, minimum, maximum, and the 95% confidence interval where appropriate. Summary statistics will be provided for baseline, the actual measurements at each visit, and the change and percent change from baseline at each visit, if applicable. All analyses will be implemented using SAS version 9.1 or higher.

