4.1.2. Study Day

If a visit/reporting date is on or after Day 1, then the study day at the visit/reporting date will be calculated as

$$\text{Day \#} = (\text{Visit/Reporting Date} - \text{Day 1 date} + 1).$$

If the visit/reporting date is before Day 1, then the study day at the visit/reporting date will be calculated as

$$\text{Day \#} = (\text{Visit/Reporting Date} - \text{Day 1 date}).$$

A study day of -1 indicates 1 day before Day 1.

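### Does the rule that stores an early stopper's coinciding visit under EOT put Week 4 or Week 8 efficacy values into the Week 12 summary?

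*Protocol*

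**What the plan says.** Protocol 8.6 requires an EOT visit both on early termination and on completing the planned treatment. If it coincides with a regular visit, "the EOT evaluations will supersede those of that scheduled visit, and the data should be entered in the EOT visit in the eCRF". The schedule in Table 3 has a single column headed "Week 12/ EOT (± 7 Days", and Protocol 4.1 says "Week 12 will correspond to the EOT". After discontinuation, Protocol 7.1.2 adds that "The date of the EOT visit should be recorded in the eCRF".

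The label reaches efficacy data by different routes. For the questionnaires, Protocol 8.2.4 says "Site staff will enter completed questionnaires into the eCRF database". Ultrasound images are "transmitted to a central vendor for reading and data summarization" (Protocol 8.2.1), and the documents do not say which visit label the returned scores carry.

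On analysis, Protocol 10.4.1 says "Efficacy assessments will be summarized using descriptive statistics at each visit", and SAP 7.2 names Weeks 4, 8 and 12 for most measures, Weeks 4 and 12 for the salivary gland ultrasound (SGUS) score, and Week 12 for ESSDAI. SAP 4.1.2 defines study day: for a visit on or after Day 1, "then the study day at the visit/reporting date will be calculated as" the visit date minus the Day 1 date plus 1. SAP 4.1.4 defines a last available value, which no visible efficacy table uses. SAP 4.1.5 leaves missing values unimputed unless a section gives a method. No visible SAP text sets efficacy visit windows or assigns an early EOT record to an analysis visit.

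**The concern.** Put the data-entry rule, the shared column and the by-visit summaries together, and a literal path appears. Someone who stops at Week 4 has that day's questionnaires entered under EOT. If the tables are built from the eCRF label, and EOT is read as Week 12, the record leaves the Week 4 summary and enters the Week 12 summary after about 4 weeks of treatment.

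Two things would be at stake. The Week 12 figures would mix treatment durations, and the Week 4 or Week 8 figures would lose a valid value. The study has about 12 participants, who are not replaced (Protocol 5.5), and the full analysis set includes everyone dosed (SAP 5.3.1), so one record is worth 1/12 = 8.3 percentage points of a proportion. In a purely descriptive study the visit summaries are the result, so it is reasonable to ask.

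**Working it through.** The plan gives no figure on this point: no dropout rate, no expected response and no nominal visit days. Its one planning figure, the chance of seeing at least 1 adverse event, reproduces (1 − 0.8^12 = 93.1%, stated as above 90%) but has no bearing here. The check is therefore a reading of the text, followed by the size under stated assumptions.

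**1. Does any rule send an early EOT record to Week 12?**
- Protocol 8.6 says where data are entered. It does not say where they are summarised.
- The Protocol 4.1 sentence pairing Week 12 with EOT describes the planned schedule. Protocol 8.6 itself separates early termination from completion and allows an EOT visit to fall on another regular visit, so EOT and Week 12 are not the same thing for an early stopper.
- The shared column allows 7 days either side. Taking Week 12 as Day 84 (assumed), its window is Days 77 to 91. An EOT visit on Day 28 is 77 − 28 = 49 days too early; one on Day 56 is 77 − 56 = 21 days too early. With Days 29, 57 and 85 the gaps are the same.
- Showing a Week 4 value as Week 12 would in effect carry it forward. SAP 4.1.5 excludes imputation unless a section specifies it, and no visible efficacy section does.

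**2. Can an analyst place the record?**
- Yes. The EOT date is recorded (Protocol 7.1.2), study day is defined (SAP 4.1.2), and treatment completion is summarised (SAP 6.2).
- This holds for ESSDAI too. Week 12 is its only named endpoint, but Table 3 collects it at Weeks 4 and 8, Protocol 10.4.1 summarises efficacy at each visit, and SAP Table 2.1.3 runs from baseline to Week 12. An early stopper's value is not forced to be either Week 12 or nothing.

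**3. How large is the effect if the label were followed?** All counts below are assumed.

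| Measure | Record placed by date | Record counted under Week 12/EOT |
|---|---|---|
| PGIC category, Week 4, 1 stopper | 6/12 = 50.0% | 5/11 = 45.5% or 6/11 = 54.5% |
| PGIC category, Week 12, 1 stopper | 5/11 = 45.5% | 5/12 = 41.7% or 6/12 = 50.0% |
| SGUS response, Week 12, 1 stopper | 4/11 = 36.4% | 4/12 = 33.3% or 5/12 = 41.7% |
| SGUS response, Week 12, 2 stoppers | 4/10 = 40.0% | 4/12 = 33.3% to 6/12 = 50.0% |

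The SGUS rows apply only if the central results inherit the eCRF label.

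Mouth dryness item (0 to 10), completers' mean change −2.0, stoppers' change between 0 and −4:
- 1 stopper: (11 × −2 + 0)/12 = −1.83 to (11 × −2 − 4)/12 = −2.17, a shift of at most 0.17.
- 2 stoppers: (10 × −2 + 0)/12 = −1.67 to (10 × −2 − 8)/12 = −2.33, a shift of at most 0.33.

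As a yardstick, the exact (Clopper-Pearson) 95% interval for 5/12 is 15.2% to 72.3%, a width of 57.1 points. One misplaced record moves the one-stopper proportions above by 5.3 points at most (36.4% to 41.7%).

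**The case for a change.** The strongest case is that two programmers could follow every visible rule and produce different Week 4, 8 and 12 tables. Early stopping is foreseeable, because the Protocol sets out discontinuation criteria. The SAP does give a rule for choosing among several laboratory values at one visit (SAP 8.3.2) but has no efficacy counterpart. It also defines a last available value that someone might be tempted to use. EOT visits need not coincide with a scheduled visit either: with nominal Days 28, 56 and 84 (assumed), Days 1 to 76 precede the Week 12 window, of which 15 + 15 = 30 fall in the Week 4 or Week 8 window and 20 + 13 + 13 = 46 in neither. And because no ultrasound is scheduled at Week 8, an EOT scan then has no scheduled slot. A few SAP sentences would settle all of this at little cost.

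The gap itself stands: the visible SAP is silent. What does not follow is that the silence does harm. Assignment by study-day window, by nominal visit, or display of early EOT as its own row are all defensible, and the choice among them is one of presentation. A window rule would also need nominal days and a tie rule, for example for a Week 4 visit on Day 24 and a separate EOT visit on Day 34. The redacted SAP text, the CRFs or the table shells may already contain such a convention.

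**Conclusion.** No change to the plan is called for. This is a missing detail that analysts can fill sensibly from what is already collected and defined. No stated rule makes an early EOT record a Week 12 value; the visit window and the no-imputation rule both point the other way.

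If the eCRF label were followed regardless, one early stopper would move a proportion by roughly 3 to 5 percentage points and the mean dryness change by at most 0.17. With nobody stopping early there is no effect. These sizes rest on assumed stopper numbers and results, since the documents give none. No hypothesis is tested (Protocol 10.3), no p-values are given (SAP 7), and the efficacy measures in SAP 7.2 are listed (SAP Appendix A, Listings 2.6.1 to 2.6.9), so a reader of the report could see where an early stopper's values went. No conclusion depends on it.

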8.7. Safety Follow-Up

The safety follow-up period is the interval between the EOT visit and the scheduled follow-up visit, which should occur 30 to 37 days after the EOT visit (or after the last dose of study drug/treatment if the EOT visit was not performed).

Adverse events and SAEs must be reported up until at least 30 days after the last dose of study drug, the date of the follow-up visit, or until toxicities resolve, return to baseline, or are deemed irreversible, whichever is longer. Reasonable efforts should be made to have the participant return for the follow-up visit and report any AEs that may occur during this period.

9. ADVERSE EVENTS: DEFINITIONS AND PROCEDURES FOR RECORDING, EVALUATING, FOLLOW-UP, AND REPORTING

9.1. Definition of Adverse Event

Adverse Event Definition

• An AE is any untoward medical occurrence associated with the use of a drug in humans, whether or not considered drug-related.• An AE can therefore be any unfavorable and unintended sign (including an abnormal laboratory finding), symptom, or disease (new or exacerbated) temporally associated with the use of study treatment.
Events Meeting the Adverse Event Definition

• Any safety assessments (eg ECG, vital signs measurements), including those that worsen from baseline, considered clinically significant in the medical and scientific judgment of the investigator (ie, not related to progression of underlying disease).• Abnormal laboratory test results constitute an AE if they are considered clinically meaningful, induce clinical signs or symptoms, require concomitant therapy, or require changes in study drug. Whenever possible, a diagnosis (eg, anemia, thrombocytopenia) should be recorded in the eCRF rather than the abnormal lab result (eg, low hemoglobin, platelet count decreased).• Exacerbation of a chronic or intermittent pre-existing condition including either an increase in frequency and/or intensity of the condition.• New conditions detected or diagnosed after study treatment administration even though they may have been present before the start of the study.

- Signs, symptoms, or the clinical sequelae of a suspected drug-drug interaction.
- Signs, symptoms, or the clinical sequelae of a suspected overdose of either study treatment or a concomitant medication. Overdose per se will not be reported as an AE/SAE unless it is an intentional overdose taken with possible suicidal/self-harming intent. Such overdoses should be reported regardless of sequelae.

Events NOT Meeting the Adverse Event Definition

- Any clinically significant abnormal laboratory findings or other abnormal safety assessments that are associated with the underlying disease, unless judged by the investigator to be more severe than expected for the participant's condition.
- The disease/disorder being studied or expected progression, signs, or symptoms of the disease/disorder being studied, unless more severe than expected for the participant's condition or considered to be treatment-related by the investigator.
- Efficacy endpoints as outlined in Section 3 will not be reported as AE/SAEs, specifically, any event that is related to disease progression of the cancer under study. Unblinded aggregated efficacy endpoint events and safety data will be monitored to ensure the safety of the participants in the study. Any suspected endpoint that upon review is not progression of the cancer under study will be forwarded to Incyte Pharmacovigilance as a SAE within 24 hours of determination that the event is not progression of the cancer under study.
- Medical or surgical procedure (eg, endoscopy, appendectomy): the condition that leads to the procedure is the AE if it occurred after signing informed consent. If present before entering the study, the condition should be captured as medical history.
- Situations in which an untoward medical occurrence did not occur (social and/or convenience admission to a hospital).
- Anticipated day-to-day fluctuations of pre-existing disease(s) or condition(s) present or detected at the start of the study that do not worsen.

9.2. Definition of Serious Adverse Event

If an event is not an AE per definition above, then it cannot be an SAE even if serious conditions are met (eg hospitalization for signs/symptoms of the disease under study, death due to progression of disease).

A Serious Adverse Event is defined as any untoward medical occurrence that, at any dose:

a. Results in death

b. Is life-threatening

The term 'life-threatening' in the definition of 'serious' refers to an adverse drug experience that places the participant, in the opinion of the initial reporter, at immediate risk of death from the adverse experience as it occurred. This does not include an adverse drug experience that, had it occurred in a more severe form, might have caused death.

c. Requires inpatient hospitalization or prolongation of existing hospitalization

In general, hospitalization signifies that the participant has been detained (usually involving at least an overnight stay) at the hospital or emergency ward for observation and/or treatment that would not have been appropriate in the physician's office or outpatient setting. Complications that occur during hospitalization are AEs. If a complication prolongs hospitalization or fulfills any other serious criteria, the event is serious. When in doubt as to whether "hospitalization" occurred or was necessary, the AE should be considered serious.

Hospitalization for elective treatment of a pre-existing condition that did not worsen from baseline is not considered an AE.

d. Results in persistent or significant disability/incapacity

- The term disability means a substantial disruption of a person's ability to conduct normal life functions.
- This definition is not intended to include experiences of relatively minor medical significance, such as uncomplicated headache, nausea, vomiting, diarrhea, influenza, and accidental trauma (eg, sprained ankle), that may interfere with or prevent everyday life functions but do not constitute a substantial disruption.

e. Is a congenital anomaly/birth defect

f. Other situations (Important Medical Event)

An event that may not result in death, be immediately life-threatening, or require hospitalization, but may be considered serious when, based on appropriate medical judgment, the event may jeopardize the participant and may require medical or surgical intervention to prevent one of the outcomes listed in the above definition. Examples of such events include invasive or malignant cancers (excluding the disease[s] under study in oncology protocols), intensive treatment in an emergency department or at home for allergic bronchospasm, blood dyscrasias, or convulsions that do not result in hospitalization, or development of drug dependency or drug abuse.

